1.2 SCHEMA

1.3 SCHEDULE OF ACTIVITIES (SOA)

Procedures	Screening Day -30 to -1	Baseline, Visit 1 Day 0	Study Visit 2 Day 7+/- 3 days	Study Visit 3 Day 30 +/-7 days	Study Visit 4 Day 90 +/- 7 days
Chart Review for screening	Х				
Measure patients for appropriate size of SB and DB		Х			
Informed consent		Х			
Complete Consent Discussion Form		Х			
Randomization		Х			
Prescribe study intervention (new DB or original SB)		Х			
Launch/retrieve data from temperature sensor in boot		х		х	х
Physical exam		Х	Х	Х	Х
Adverse event review			Х	Х	Х
Administer surveys		Х		Х	Х
Video record patients in their prescribed bar				х	

Procedures	Screening Day -30 to -1	Baseline, Visit 1 Day 0	Study Visit 2 Day 7 +/- 3 days	Study Visit 3 Day 30 +/-7 days	Study Visit 4 Day 90 +/- 7 days
Distribute/collect brace wear log		Х		Х	Х
Document on study enrollment log	Х	Х	Х	Х	Х

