4 STUDY DESIGN

4.1 OVERALL DESIGN

This is an assessor-blinded randomized controlled trial in which patients with well-corrected idiopathic clubfoot will be randomized to wear either their original SB (which is standard care for clubfoot treatment) or the new DB for 30 days. After 30 days, all participants will resume use of the SB and be monitored for an additional 60 days.

This study is a "feasibility trial" as it is assessing the feasibility of conducting a large-scale randomized controlled trial to evaluate the effectiveness of the DB. As such, feasibility will be determined by the ability to recruit patients within the goal study period and to retain participants.

On Day 0 of the study period, patients will be randomized and receive baseline clinical and questionnaire evaluations. A temperature sensor will be added in each participant's boots during the 90-day study period to objectively measure time of brace wear.

All patients will be evaluated after 7 days in their assigned bar to check for brace fit, any complications, and to perform required adjustments. This 7-day checkup is standard care for clubfoot treatment when patients receive the SB and FAB for the first time.

After 30 days, the patients wearing the DB will resume use of the SB. All patients will be seen at the end of the first 30 days and after 90 days to monitor for recurrence of the clubfoot deformity, complications of brace wearing, and parent-reported perception of their child's comfort with the FAB. Parents will also be asked to complete a self-reported brace wear log that will be collected on Day 30 and 90.

A minimum of 10 patients per arm will be recruited. Once there are 10 in each arm, recruitment will halt. It is hypothesized that patients using the DB will experience higher brace tolerance as measured by the temperature sensors, and higher comfort levels as reported by parents, without an increase in clubfoot deformity recurrence compared to the SB.

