To compare the range of motion provided by the SB to the DB, and to verify that the DB consistently maintains proper foot position and leg alignment during use, parents will be given the option of consenting to video recordings being taken during the hospital visit of the patient's feet and legs while wearing their prescribed bar. This recording will occur on Day 30 of the study period by a member of the study team. These videos will be closely studied to compare the range of motion provided by the SB to the DB, and to verify that the DB consistently maintains proper foot position and leg alignment during use. Note that audio will be removed from the videos.

Patient recruitment will be documented in an electronic enrollment log. To evaluate ease of recruitment, this enrollment log will also include patients who do not wish to participate in the study and their reason(s) for refusal. The enrollment log will also record information on patients that do not adequately fit the available prototype but are otherwise eligible, including patient age and fit issues. This will serve to inform future adaptations of the new DB.

During the intervention period, all patients will be monitored for brace fit by the PI and/or physiotherapist [name]. A blinded outcomes assessor will clinically evaluate all patients to assess foot shape for possible recurrence or complications. The outcomes assessor will be a skilled clubfoot provider and will not be made aware of which bar was provided to the patient and is

independent of the design team. Once the trial is complete, the patient's care will resume with their primary clubfoot provider.

Clubfoot patients are normally reviewed in clinic every 3-6 months. If scheduling permits, Day 0 of the study period will align with patient's already scheduled follow up visit. All patients will therefore require either 3 or 4 extra visits (possibly on Day 0, and surely on Day 7, Day 30, and Day 90). These extra visits will consist of the same evaluations done in the routine clubfoot monitoring protocol, in addition to the study-related questionnaire, brace wear log, video recording (on Day 30 only), and temperature sensor data collection.

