4.2 SCIENTIFIC RATIONALE FOR STUDY DESIGN

This trial design allows for direct comparison between SBs and the new DB, without affecting the patient's long-term treatment plan or outcomes. The assessments will be between patients (control vs. experimental cohorts) and within the same patient (experimental cohort wearing both bar designs).

Since participants in this feasibility trial will only use the DB for a maximum of 1 month, the likelihood of finding a difference in bar effectiveness is quite low. Therefore, following this feasibility trial, the study team plans to conduct a prospective randomized controlled trial of the novel DB versus standard bars, comparing the DB's effectiveness at maintaining ideal foot position and preventing recurrence over a minimum two-year period. A separate REB application will be filed for this trial.

Bias in brace wear reporting will also be mitigated in this feasibility study by using temperature sensors to objectively measure the time of brace wear, and by using quantitative evaluations done by blinded outcomes assessors to evaluate study endpoints.

To mitigate the risk of bias in the completion of the parent-reported surveys, the surveys were written using neutral language as much as possible. For example, instead of using the terms "standard" and "dynamic," the bar types were described using the terms "current," "original," and "alternative."

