If consent is provided by the parents, a member of the study team will also record a video of each patient wearing their prescribed bar on Day 30 of the study period. These videos will be closely studied to compare the range of motion provided by the SB to the DB, and to verify that the DB consistently maintains proper foot position during use. Videos will be recorded on a password-protected personal device, audio will be removed, then the video will be uploaded each day to the patient's REDCap forms. The video will then be deleted from the personal device. All efforts will be made to made to only include the patient's feet and legs in the field of the video, and to blur or remove any identifiable physical marks like unique birthmarks and tattoos on the patient's skin.

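### The Day 30 videos compare SB and DB range of motion only between different children; a second clip in the SB for children still using the DB would add a within-child comparison at little cost

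*Combined protocol and SAP*

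**What the plan says.** Section 9.3.3 provides that, where parents consent, a team member will "record a video of each patient wearing their prescribed bar on Day 30 of the study period". It gives the purpose as follows: "These videos will be closely studied to compare the range of motion provided by the SB to the DB". A second purpose is to check that the DB holds the foot in position. Section 4.1 repeats both purposes, makes the video optional and limits it to one visit: "video recording (on Day 30 only". In the Schedule of Activities (section 1.3) the row "Video record patients in their prescribed bar" has a single mark, in the column "Study Visit 3 Day 30 +/-7 days".

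On the bars themselves, section 4.1 says: "After 30 days, the patients wearing the DB will resume use of the SB". On numbers it says: "A minimum of 10 patients per arm will be recruited". Section 4.2 states that assessments will be made between patients and also "within the same patient (experimental cohort wearing both bar designs". Section 9.3.1 limits the analysis to descriptive statistics. No section schedules an SB recording of a DB child, and none says how range of motion will be measured from the footage.

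**The concern.** The question put to the videos is about the bars: how much movement does each allow? As scheduled, DB children are filmed only in the DB and control children only in the SB. Any difference seen therefore mixes the effect of the bar with differences between children in size, strength and activity on the day. The inclusion range of 1 to 3 years makes those differences potentially large, and each arm has about 10 children, fewer if some parents decline the optional video.

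The added leg mobility is the mechanism by which the DB is expected to improve comfort and tolerance (section 2.2), and the video is the only planned recording from which the two bars' range of motion is to be compared. The Day 30 visit falls around the time DB children change back to the SB, so a same-day recording in the second bar is within reach and is not planned.

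**Working it through.** **What the schedule can deliver**

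- Filming occasion: Day 30 only, in the prescribed bar (sections 1.3, 4.1, 9.3.3).
- DB arm: clip in the DB, no clip in the SB. Control arm: clip in the SB.
- Available contrast: DB children against other children in the SB. No within-child contrast is possible from the video.

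**Precision of the two designs**

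The plan states no SD, precision or sample size for range of motion, so there is no figure of its own to reproduce. The comparison below is in SD units.

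Inputs: n = 10 per arm (section 4.1), taking every family as consenting to video (assumption); the same between-child SD in both bars (assumption); within-child correlation r between the two bars of 0.3, 0.5 or 0.7 (assumption).

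Unpaired 95% half-width = t(0.975, 2n−2) × √(2/n) = 2.101 × √0.2 = 2.101 × 0.447 = **0.94 SD**.

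Paired 95% half-width = t(0.975, n−1) × √(2(1−r)/n), with t(0.975, 9) = 2.262:

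| r | √(2(1−r)/10) | Half-width (SD) | Change from 0.94 |
|---|---|---|---|
| 0 | 0.447 | 1.01 | 8% wider |
| 0.3 | 0.374 | 0.85 | 10% narrower |
| 0.5 | 0.316 | 0.72 | 24% narrower |
| 0.7 | 0.245 | 0.55 | 41% narrower |

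Break-even correlation = 1 − (2.101/2.262)² = **0.14**. Below it, the loss of degrees of freedom outweighs the pairing.

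**Fewer consenting families** (numbers assumed)

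| n per arm | Unpaired (SD) | Paired, r = 0.5 (SD) | Break-even r |
|---|---|---|---|
| 7 | 1.17 | 0.93 | 0.21 |
| 5 | 1.46 | 1.24 | 0.31 |

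**If the SDs are not equal**

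Section 6.1 describes a straight SB as rigid, and section 2.1 says most standard bars greatly restrict independent knee and hip movement. Motion in the SB may then be near its floor, with little spread. Illustration (assumption): SB SD one tenth of DB SD, r = 0.5, n = 10, in units of the DB SD.

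- Unpaired (Welch): SE = √((1 + 0.01)/10) = 0.318; df = 9.18; t = 2.255; half-width = 0.72.
- Paired: SE = √((1 + 0.01 − 2 × 0.5 × 0.1)/10) = √0.091 = 0.302; t = 2.262; half-width = 0.68.
- Gain: 1 − 0.682/0.717 = about **5%**.

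The precision gain therefore runs from nothing or slightly negative, through about 5%, to about 40%, depending on quantities the documents do not give.

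**The case against.** The strongest reply is that precision is not the aim. Range of motion is not among the objectives or endpoints in section 3, the analysis is descriptive, no decision depends on the difference, and the second purpose of the footage, checking foot position in the DB, is fully met by the present plan. This stands, and it keeps the point minor. It does not remove the point, because the comparison of the two bars is a stated purpose, and a mean within-child difference is as descriptive as a difference between arms.

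The reply that the precision gain is uncertain also stands, as the 5% illustration shows.

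Three stronger readings are tempting, and the documents do not support them.

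- *The plan breaks a promise of within-patient comparison.* Section 4.2 speaks of assessments in general and names neither video nor range of motion. The surveys at Day 0, 30 and 90 (section 8.1) and the sensors and logs kept through Day 90 (sections 4.1 and 6.4) already give DB children data in both bars.
- *Every DB child could be filmed in both bars at Day 30.* A child whose DB broke beyond quick repair (section 7.2) or who showed recurrence (section 2.3) may already be back in the SB. With DB use of at most one month (section 4.2) and a 7-day window either side of the visit, others may be too. Nothing says that families bring the SB to the visit.
- *Optional filming will unbalance the arms.* The documents do not say when video consent is taken. The Schedule of Activities lists informed consent at Day 0, ahead of randomization; if video consent is part of it, the choice cannot depend on the arm.

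Finally, it might seem economical to drop the control clips once DB children are filmed twice. That would be a mistake: control children are the only ones filmed who have worn the SB throughout, whereas an SB clip taken after 30 days in the DB may show a child readjusting.

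**Conclusion.** The concern holds in limited form. As scheduled, the comparison of range of motion between SB and DB is solely between different children, and a same-visit second clip would allow a within-child comparison as well. The main benefit is that the same legs are seen in both bars on the same day. The gain in precision is secondary: at n = 10 with equal SDs the half-width falls from 0.94 SD to between 0.85 and 0.55 SD for correlations of 0.3 to 0.7, but both the correlation and the equality of SDs are assumptions. The measurement is optional, descriptive and outside the listed endpoints, so this is a cheap improvement and not a flaw in the trial's primary feasibility objective.

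**What to change.** In the Schedule of Activities, section 4.1 and section 9.3.3, state that at the Day 30 visit each consenting child still using the DB will be filmed in the DB and also in their own SB, with the order alternated from child to child. Ask these families to bring the SB to the visit. In section 9.3.3, report the within-child difference in range of motion descriptively, with the number of children it rests on, and keep the control-arm clips as the between-child comparison in children accustomed to the SB. Add a line on the second clip to the optional video consent.

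The cost is a few lines of text, one extra bar change and one short clip per DB child, at a visit that already includes the exam, survey, log collection and sensor readout. No extra visit is needed, and the prescribed bar does not change. Alternating the order deals with sequence within the visit but not with 30 days of habituation to the DB, so the SB clip of a DB child should be reported with that caveat.

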10 SUPPORTING DOCUMENTATION AND OPERATIONAL CONSIDERATIONS

10.1 REGULATORY, ETHICAL, AND STUDY OVERSIGHT CONSIDERATIONS

10.1.1 STUDY DISCONTINUATION AND CLOSURE

This study may be temporarily suspended or prematurely terminated if there is sufficient reasonable cause. Written notification, documenting the reason for study suspension or termination, will be provided by the suspending or terminating party to study participants and the REB. Study participants will be contacted, as applicable, and be informed of changes to study visit schedule.

Circumstances that may warrant termination or suspension include, but are not limited to:

- Determination of unexpected, significant, or unacceptable risk to participants by use of the dynamic bar
- Insufficient compliance to protocol requirements
- Data that are not sufficiently complete and/or evaluable

The study may resume once concerns about safety, protocol compliance, and data quality are addressed, and satisfy the Sponsor and REB.

10.1.2 CONFIDENTIALITY AND PRIVACY

All research activities will be conducted in as private a setting as possible.

Study data will be entered into REDCap, a secure, web-based application designed exclusively to support data capture for research studies. The application and data are housed on servers provided by the Hospital for Sick Children. These servers are located within SickKids secure data center.

Most patient health information that will be analyzed for this trial will be collected, stored, and destroyed as specified by the Clubfoot Research Registry (REB #1000053919). The clinical evaluations performed at each study visit will be standard care.

A separate electronic enrollment log will track enrollment of patients by MRN number and name and assign a study ID to those patients that consent to participate in the trial. Data collected will not link to participants' OHIP number.

Patient confidentiality will be ensured except when legally required. Only members of the research team will have access to the research data. Any data exported for statistical analysis will be de-identified. All identifying information will be kept behind 2 security measures or as per equivalent institutional policy, under the supervision of the PI and will not be transferred outside of the hospital.

To enable evaluations and/or audits from the Sponsor or REB, the Principal Investigator agrees to keep records, including all original signed informed consent forms, consent discussion forms, the enrollment log, and surveys in a secure location for a minimum of 7 years in accordance with SickKids policy. Subsequently, all identifying data will be destroyed.

10.1.4 SAFETY OVERSIGHT

Safety oversight will be under the direction of a Data Safety Monitoring Board (DSMB) composed of individuals with the appropriate expertise, including a pediatric orthopaedic surgeon who is familiar with clubfoot treatment. Members of the DSMB will be independent from the study conduct. The DSMB will meet one time during the 90-day study period to assess safety and efficacy data on each arm of the study. The DMSB will operate under the rules of an approved charter that will be reviewed at the

organizational meeting of the DSMB. At this time, each data element that the DSMB needs to assess will be clearly defined. The DSMB will provide its input to the Hospital for Sick Children.

10.1.5 PROTOCOL DEVIATIONS

A protocol deviation is any noncompliance with the clinical trial protocol. The Principal Investigator will assure that no deviation from, or changes to the protocol will take place without prior agreement from the Sponsor and documented approval from the Research Ethics Board (REB), except where necessary to eliminate an immediate hazard(s) to the trial participants. The noncompliance may be either on the part of the participant, the Investigator, or the study site staff. As a result of deviations, corrective actions are to be developed by the site and implemented promptly. All protocol deviations will be documented; the Principal Investigator will assess each protocol deviation to determine the impact to the patient's rights, safety or welfare, study efficacy and data integrity.

It is the responsibility of the Principal Investigator to use continuous vigilance to identify and report deviations within 10 working days of identification of the protocol deviation, or within 10 working days of the scheduled protocol-required activity. All deviations must be addressed in study source documents and reported to the Sponsor. Protocol deviations must be sent to the reviewing REB in accordance with their policies. The Principal Investigator is responsible for knowing and adhering to the reviewing REB requirements.

10.1.6 CONFLICT OF INTEREST POLICY

There is a conflict of interest wherein the PI and co-investigators of this study are the inventors of the dynamic bar, and so they might wish to sell the bar in the future for profit. This conflict of interest will be mitigated by relying on unbiased quantitative evaluations done by blinded outcomes assessors in order to assess the study's endpoints.

There is also a potential pre-existing health care provider-patient relationship between members of the care team and the participant. However, this potential conflict of interest will be mitigated through exclusion of the circle of care team from the informed consent process. The research assistant and/or research coordinator will be responsible for obtaining informed consent.

10.2 ABBREVIATIONS

AE	Adverse Event
DB	Dynamic Bar
DSMB	Data Safety Monitoring Board
FAB	Foot Abduction Brace
GCP	Good Clinical Practice
ICH	International Council on Harmonisation
NIST	National Institute of Standards and Technology
PI	Principal Investigator
REB	Research Ethics Board
REDCap	Research Electronic Data Capture
SAE	Serious Adverse Event
SB	Standard Bar
SoA	Schedule of Activities

12 APPENDIX A: IMAGES OF FOOT ABDUCTIONS BARS

Figure 1: Standard Dobbs Bar (23)

Figure 2: Standard Ponseti Straight Bar with "Quick Clip" mechanism (16,17).

Figure 3: Novel Dynamic Bar Prototype.

13 APPENDIX B: SURVEYS USED IN INITIAL EVALUATION

New Dynamic Clubfoot Brace

Parent Survey

Thank you for agreeing to try out our new clubfoot brace. Please fill out this questionnaire so that we can improve your child's experience with their treatment. We welcome your comments.

My child is c	omfortable i	n their curre	nt brace	
□ 1 Strongly Disagree	□ 2 Disagree	□ 3 Unsure	□ 4 Agree	□ 5 Strongly Agree
I have conc	erns about n	ny child's cu	rrent brace	n s
□ 1 Strongly Disagree	□ 2 Disagree	□ 3 Unsure	□ 4 Agree	□ 5 Strongly Agree
Based on fir like my child	st impressions I's current bro	a, I like this ne	ew brace m	ore than I
□ 1 Strongly Disagree	□ 2 Disagree	□ 3 Unsure	□ 4 Agree	□ 5 Strongly Agree
My child see than they a	ems to be mo re in their cur	ore comforto rent brace	able in this n	iew brace
□ 1	□ 2	□ 3	□ 4	□ 5
Strongly Disagree	Disagree	Unsure	Agree	Strongly Agree
l feel that m brace	y child move	s their feet r	more naturo	ally in this
□ 1 Strongly Disagree	□ 2 Disagree	□ 3 Unsure	□ 4 Agree	□ 5 Strongly Agree
I would pref more freedo	er that my ch om to move t	hild uses a b heir feet (lik	race that g e this new b	ives them prace)
□ 1	□ 2	□ 3	□ 4	□ 5
Strongly Disagree	Disagree	Unsure	Agree	Strongly Agree
Do you hav	e any conce	rns with this	new brace	Ş
		Yes 🗆 No	0	
If yes, please	e specify:			
Please prov have:	ide any addi	tional feedb	ack that yo	ou might

New Dynamic Clubfoot Brace

Physiotherapist/Orthotist Survey

Thank you for telling your patient about our new clubfoot brace. Please fill out this questionnaire so that we can improve patient experience. We welcome your comments.

How old is the patient? (months)

How long has the patient been in a brace? Patient seems to be more comfortable in this new brace

than they are in their current brace							
□ 1 Strongly Disagree	□ 2 Disagree	□ 3 Unsure	□ 4 Agree	□ 5 Strongly Agree			
Leg alignment is well maintained in this new brace							
□ 1 Strongly Disagree	□ 2 Disagree	□ 3 Unsure	□ 4 Agree	□ 5 Strongly Agree			
Correction c	of the foot is v	well maintai	ned in this r	new brace			
□ 1 Strongly Disagree	□ 2 Disagree	□ 3 Unsure	□ 4 Agree	□ 5 Strongly Agree			
Patient exte	nds their legs	independe	ently in this r	new brace			
□ 1 Strongly Disagree	□ 2 Disagree	□ 3 Unsure	□ 4 Agree	□ 5 Strongly Agree			
Patient rotat in this new b	es their feet race	independer	ntly in the so	agittal plane			
□ 1 Strongly Disagree	□ 2 Disagree	□ 3 Unsure	□ 4 Agree	□ 5 Strongly Agree			
It is just as ea this new bra	isy to attach ce as it is in c	the bar to t other standa	the patient' ard braces	s boots in			
□ 1 Strongly Disagree	□ 2 Disagree	□ 3 Unsure	□ 4 Agree	□ 5 Strongly Agree			
It is just as easy to make adjustments to this new brace as it is to make adjustments to other standard braces							
□ 1 Strongly Disagree	□ 2 Disagree	□ 3 Unsure	□ 4 Agree	□ 5 Strongly Agree			
Do you have	e any conce	rns with this	new brace?	Ş			

Figure 4: Surveys administered in the initial, informal evaluation of the dynamic bar.
